3 OBJECTIVES

3.1 Study Objectives

Primary:

- To evaluate the safety and tolerability of single-vial lyophilized ID93 + GLA-SE following two intramuscular (IM) injections administered on Days 0 and 56.
- To compare the safety and tolerability of single-vial lyophilized ID93 + GLA-SE to the two-vial presentation consisting of lyophilized ID93 and liquid GLA-SE following two IM injections administered on Days 0 and 56.

Secondary:

- To assess the immunogenicity of single-vial lyophilized ID93 + GLA-SE following two IM injections administered on Days 0 and 56 by quantifying cytokine production and IgG antibody responses to ID93 at specified time points.
- To compare the immunogenicity of single-vial lyophilized ID93 + GLA-SE to the two-vial presentation consisting of lyophilized ID93 and liquid GLA-SE following two IM injections administered on Days 0 and 56.

Exploratory:

- To further evaluate the immunogenicity of ID93 + GLA-SE following two IM injections administered on Days 0 and 56 by measuring mycobacterial growth inhibition, quantifying IgA levels in mucosal secretions, and measuring frequencies of circulating T follicular helper cells, antibody secreting cells, and memory B cells at specified time points.

3.2 Study Outcome Measures

3.2.1 Primary Outcome Measures

- The number of subjects experiencing solicited local injection site reactions within 7 days following each study injection.
- The number of subjects experiencing solicited systemic reactions within 7 days following each study injection.
- The number of subjects spontaneously reporting adverse events from Day 0 through Day 84.
- The number of serious adverse events considered related to any of the study injections reported at any point during the study period.

3.2.2 Secondary Outcome Measures

- The proportion of subjects with at least a 4-fold increase in IgG antibody responses to ID93 on Days 14, 56, 70, 84, and 224 relative to baseline (Day 0).
- Mean fold change from baseline (Day 0) in IgG antibody responses to ID93 on Days 14, 56, 70, 84, and 224.
- The number of IFN- γ and IL-10 cytokine-secreting cells in PBMC samples in response to the ID93 antigen relative to baseline (Day 0) at Days 14, 56, 70, 84, and 224, as assayed by ELISpot.
- Percentage of CD4 and CD8 T cells producing 1 or more cytokines (IFN- γ , TNF, and IL-2) simultaneously in response to stimulation with the ID93 antigen as measured by intracellular cytokine staining of PBMCs at Days 14, 56, 70, 84, and 224 relative to baseline (Day 0).

3.2.3 Exploratory Outcome Measures

- Measurement of net intracellular growth inhibition of Mtb using whole blood on Days 0, 70, and 224.
- Quantitate IgA titers in mucosal secretions (nasal swabs and tear collections) by ELISA on Days 0, 70, and 224.
- Quantitate number of antibody-secreting cells in PBMC by short-culture B cell ELISpot on Days 0, 7, and 63.
- Quantitate number of antigen-specific memory B cells in PBMC by long-culture B cell ELISpot on Days 0, 56, 84, and 224.
- Quantitate T follicular helper cells, memory B cells, and T cell homing markers in PBMC by immunophenotyping flow cytometry on Days 0, 7, 14, 63, 70, and 224.

4 STUDY DESIGN

This study is a phase 1, randomized, double-blind clinical trial designed to evaluate the safety, tolerability, and immunogenicity of single-vial lyophilized ID93 + GLA-SE compared to the two-vial presentation consisting of lyophilized ID93 and liquid GLA-SE administered as two intramuscular injections in healthy adult subjects.

This study will enroll 48 healthy subjects aged 18 to 55. Subjects will be counseled on the study and will then give an informed consent. Screening will be performed that will include evaluation of medical history, medication history, a physical examination, and safety laboratory evaluations. Subjects who meet all eligibility criteria will be randomized 1:1 into the two treatment groups. Study injections will be performed and subjects will be observed in clinic for 60 minutes. All subjects will complete a written subject memory aid that solicits local and systemic reactogenicity adverse events for 7 days following each study injection. Subjects will undergo a second study injection on Day 56. General safety will be evaluated on Days 0, 7, 56, 63, and 84 for each subject. All data will be recorded in the source document during the study period.

Non-serious adverse events will be collected through Day 84 (28 days following the last study injection). The occurrence of serious adverse events (SAEs) and the new onset of any potential immune-mediated medical conditions (PIMMCs) will be collected throughout the study period (approximately 421 days).

The details of all study visits are outlined in [Section 7](#). Each subject's duration of participation will be about 14 months. A detailed outline of the study visits and procedures is provided in the Study Visit Schedule ([Appendix 1](#)). Immunogenicity will be assessed on Day 0 (pre-dose) and on Days 7, 14, 56, 63, 70, 84, and 224. Blood will be assessed for safety laboratories on the day of screening, and on Days 7 and 63. Urinalysis will be performed at screening.

5 STUDY ENROLLMENT AND WITHDRAWAL

Forty-eight (48) subjects between the ages of 18 and 55 years will be enrolled over an estimated 4 month period. It is the intent of this study to enroll subjects who are considered healthy volunteers. Subjects with pre-existing clinically significant conditions are not considered normal, healthy volunteers. The target population will reflect the community at large in the Saint Louis area. Various methods of recruitment may be used such as letters, postcards, e-mails, brochures, posters, media boards, websites, social media, telephone contact, advertisements, and press releases. All forms and mechanisms of recruitment as well as the recruitment materials will be approved by the site's IRB prior to use. Retention of participants is accomplished through study reminder telephone calls, texts, emails, and mailings as per the preferences of each individual volunteer.

5.1 Subject Inclusion Criteria

Subjects must meet ALL of the following criteria to be eligible for inclusion in the study:

1. Males and females 18 to 55 years of age.
2. In good general health as confirmed by a medical history and physical exam, vital signs*, and screening laboratories conducted no more than 30 days prior to study injection administration.

**Temperature <38 ° C, respiratory rate < 17 breaths pm, heart rate ≤100 bpm and >54 bpm, systolic blood pressure ≤140 mmHg and >89 mmHg, diastolic blood pressure ≤90 mmHg and ≥60 mmHg.*

NOTE: Athletically trained subjects with a pulse ≥40 may be enrolled at the discretion of the principal investigator or designated licensed clinical investigator.

3. Screening laboratory values within normal limits: sodium, potassium, ALT, AST, total bilirubin, alkaline phosphatase, creatinine, random glucose, total WBC count, hemoglobin, and platelet count.
4. Negative HIV 1/2 antibody, hepatitis B surface antigen (HBsAg), and hepatitis C virus (HCV) antibody.
5. Urine dipstick for protein and glucose (negative to trace protein are acceptable).
6. Women of childbearing potential* in sexual relationships with men must agree to practice acceptable contraception** for the 30-day period before Day 0 through 90 days after the last study injection.

**Not sterilized via tubal ligation, bilateral oophorectomy, hysterectomy or successful Essure® placement (permanent, non-surgical, non-hormonal sterilization) with documented radiological confirmation test at least 90 days after the procedure, and still menstruating or < 1 year of the last menses if menopausal). Post-menopausal defined as at least 12 months spontaneous amenorrhea and confirmed with FSH > 40 mIU/ml.*

***Includes, but is not limited to, sexual abstinence, monogamous relationship with vasectomized partner who has been vasectomized for 6 months or more prior to the subject receiving study product, barrier methods such as condoms or diaphragms with spermicide or foam, effective intrauterine devices, NuvaRing®, and licensed hormonal methods such as implants, injectables or oral contraceptives ("the pill").*

7. Able to understand and comply with planned study procedures and willing to be available for all study-required procedures, visits and calls for the duration of the study.
8. Provide written informed consent before initiation of any study procedures.
9. Willing to abstain from donating whole blood or blood derivatives until 90 days after the final study injection.

5.2 Subject Exclusion Criteria

Subjects who meet any of the following criteria at screening/baseline will be excluded from study participation:

1. Previous exposure to ID93 vaccines or experimental products containing GLA-SE.
2. History of treatment for active or latent tuberculosis infection.
3. History or evidence of active or documented latent tuberculosis, or positive QuantiFERON®-TB Gold test.
4. Shared a residence within the last year prior to randomization with an individual on anti-tuberculosis treatment or with culture or smear positive tuberculosis.
5. Received a tuberculin skin test within 3 months (90 days) prior to randomization.
6. History of autoimmune disease or immunosuppression.
7. Used immunosuppressive medication (e.g., oral or injected steroids) within 3 months prior to randomization (inhaled and topical corticosteroids are permitted).
8. Received any investigational drug therapy or investigational vaccine within past 6 months prior to randomization, or planned participation in any other investigational study during the study period.
9. Received investigational TB vaccine at any time prior to randomization.
10. Received any vaccine within 30 days prior to the first study vaccination and no planned immunizations between Day 0-84 or Day 210-224 due to the washout period prior to immunology blood draws.
11. History or laboratory evidence of immunodeficiency state including but not limited to laboratory indication of HIV-1 infection at screening.

12. History of allergic disease or reactions, likely to be exacerbated by any component of the study vaccine.
13. History of allergic reaction to kanamycin-related antibiotics.
14. Subjects with a history of previous anaphylaxis or severe allergic reaction to vaccines or unknown allergens.
15. Previous medical history that may compromise the safety of the subject in the study, including but not limited to: severe impairment of pulmonary function from tuberculosis infection or other pulmonary disease; chronic illness with signs of cardiac or renal failure; suspected progressive neurological disease; or uncontrolled epilepsy or infantile spasms.
16. Known or suspected alcohol or drug abuse within the past 5 years.
17. Smokes 1 pack or more of cigarettes per day.
18. History of keloid formation or excessive scarring.
19. History or evidence on physical examination of any systemic disease or any acute or chronic illness that, in the opinion of the investigator, may interfere with the evaluation of the safety or immunogenicity of the vaccine, including axillary lymphadenopathy.
20. Received a blood transfusion or immunoglobulin within the past 3 months prior to randomization.
21. Donated blood products (platelets, whole blood, plasma, etc.) within past 1 month prior to randomization.
22. Presence of any febrile illness, oral temperature of >100.4 °F/ 38.0 °C within 24 hours of study injection administration. Such subjects may be re-evaluated for enrolment after resolution of illness.
23. Positive serum (at screening visit only) or urine pregnancy test at screening or within 24 hours prior to study injection for women of childbearing potential.
24. Breastfeeding at any time throughout the study.
25. Rash, tattoos, or any other dermatological condition on the upper anterolateral arm that could adversely affect the vaccine injection site or interfere with its evaluation.
26. BMI <18 or >35 kg/m².
27. Any medical or neuropsychiatric condition which, in the Investigator's opinion, would render the subject incompetent to provide informed consent or unable to provide valid safety observations and reporting.

28. Cancer or treatment for cancer within 3 years of study injection administration. Persons with a history of cancer who are disease-free without treatment for 3 years or more are eligible. Persons with treated and uncomplicated basal cell carcinoma of the skin are eligible.

29. Subjects unlikely to cooperate with the requirements of the study protocol.

Vital signs are performed after subjects have been in a seated position for five minutes, with no hot or cold beverages or smoking in the past five minutes. Vital signs may be performed up to three times to allow for transient conditions to resolve. Screening laboratory values that are abnormal, but are considered abnormal due to an acute illness or process may be repeated once. Creatinine, AST, ALT, bilirubin values that fall below the FDA standard toxicity tables ([Appendix 3 - Guidance for Industry: Toxicity Grading Scale for Healthy Adult and Adolescent Volunteers Enrolled in Preventative Vaccine Clinical Trials; FDA/CBER; 2007](#)) are not considered abnormal for the purposes of this study. Additionally, abnormalities in the RBC parameters other than hemoglobin and abnormalities in the WBC differential not specified in the inclusion criteria above (e.g. low lymphocytes, basophils, or eosinophils) will not be considered exclusionary for this study and will be followed with the standard safety laboratory follow ups outlined in the study. Laboratory values that are performed as a standard panel by the clinical laboratory, but are not requested for the study, will be reviewed by a licensed study clinician and the clinician will determine whether the laboratory value abnormality is clinically significant and should be considered exclusionary. If determined to be clinically insignificant, the study team is not required to follow the laboratory until resolution or the value is determined to be clinically stable.

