6.5 Concomitant Medications/Treatments

Administration of any medications, therapies, or vaccines will be documented in the subject's source documentation and reported on the subject's electronic case report form (eCRF). Concomitant medications will include all medications, vitamins, and supplements taken within the 30 days before enrollment and through 28 days after the last study injection (approximately Day 84) or early termination, whichever occurs first.

Medications that might interfere with the evaluation of the investigational product should not be used unless necessary. Medications in this category include, but are not limited to, glucocorticoids (i.e., oral, parenteral, and high-dose inhaled steroids), and immunosuppressive or cytotoxic drugs. Analgesics and antipyretics should be avoided for the 24 hours following study injection, unless necessary.

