7.8 Day 84 (± 5) Evaluation

- Obtain vital signs (BP, P, RR, oral temperature).
- Perform a targeted physical exam if indicated, based on symptoms.
- Review adverse events, including SAEs and PIMMCs.
- Review concomitant medications.
- Collect blood for:
 - Serum for IgG ELISA
 - PBMC isolation

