7.9 Day 224 (± 10) Evaluations

- Perform a targeted physical exam if indicated, based on symptoms.
- Review SAEs and PIMMCs.
- Record concomitant medications used for treatment of SAEs or PIMMCs, if any.
- Collect nasal swab
- Collect tears
- Collect blood for:
 - Serum for IgG ELISA
 - Whole blood for MGIA
 - PBMC isolation

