8 STUDY PROCEDURES AND EVALUATIONS

8.1 Clinical Evaluations

The schedule of study visits and procedures is specified in [Appendix 1](#).

Medical History: Will be obtained by interview of the subjects. Subjects will be queried regarding a history of significant medical disorders of the head, eyes, ears, nose, throat, mouth, cardiovascular system, lungs, gastrointestinal tract, liver, pancreas, kidney, nervous system, blood, lymph glands, endocrine system, musculoskeletal system, skin, and genital/reproductive tract. A history of any allergies, cancer, immunodeficiency, psychiatric illness, substance abuse, and autoimmune disease will be solicited. The collection of medical history information will include a review of TB vaccine history and plans for vaccinations.

Concomitant Medications: All current medications and medications taken in the 30 days before enrollment (prescription and over-the-counter drugs) will be included, as well as vitamins and supplements, through 28 days after the last study injection, unless if used for treatment of an SAE or PIMMC. In the latter case, it will be included through the end of the study. Assessment of eligibility also will include a review of prohibited medications (per the exclusion criteria).

Physical Examination: This examination will be conducted at Screening and will assess general appearance including height and weight (at Screening only), vital signs (blood pressure, oral temperature, pulse), and the following areas/symptoms: skin, lymph nodes, head, eyes, ears, nose, throat, neck, respiratory, cardiovascular, pulmonary, abdomen, extremities, musculoskeletal, and neurological.

Targeted Physical Examination: This may be conducted at any study visit based on indicated symptoms. No examination is necessary if no symptoms are present.

Local and systemic reactogenicity assessments: This will include a brief review for assessment of AEs, which includes an assessment of pain, erythema, and induration at the injection site; and systemic reactions including headache, arthralgia, chills, loss of appetite, fever, fatigue, and myalgia.

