Appendix 1: Schedule of Study Visits and Procedures

	Screen	Schedule for Study Injection Phase (Days with allowable visit window)						Follow-Up			ET ¹ visit
		visit	visit	phone	visit	visit	phone	visit	visit	phone	
	Day -30 to Day 0	0	7 (±1)	14 (±3)	56 (±3)	63 (±1)	70 (±3)	84 (±5)	224 (±10)	421 (±14)	
Informed consent	X										
Inclusion/exclusion criteria	X	X			X						
Medical history	X										
Concomitant medications	X	X	X		X	X		X	(X) ⁶	(X) ⁶	X
Physical exam	X										
Targeted physical exam ⁵		X	X		X	X		X	X		X
Vital signs	X	X ²	X		X ²	X		X			X
Safety labs	X		X			X					
HIV, HCV, HBsAg	X										
Urinalysis (protein, glucose)	X										
Serum pregnancy test or FSH ³	X										
Urine pregnancy test		X			X						
Visual acuity	X										
QuantiFERON®-TB Gold	X										
Nasal swab and tear collection		X					X		X		(X) ⁷
Immunology blood ⁴		X	X	X	X	X	X	X	X		(X) ⁷
Study injection		X			X						
Injection site checks		X	X		X	X					
Dispense memory aid		X			X						
Review memory aid			X			X					
Adverse events	X	X	X		X	X		X			X
SAE/PIMMC	X	X	X		X	X		X	X	X	X

¹ ET = Early termination

² Vital signs are performed prior to and at 60 minutes post study injection.

³ Serum pregnancy test for females of childbearing potential; FSH for post-menopausal females

⁴ See Appendix 2 for volumes of immunology blood.

⁵ If indicated, based on review of symptoms

⁶ Concomitant meds to be collected only if used for treatment of an SAE or PIMMC.

⁷ If indicated

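### The fixed Day 210-224 vaccine washout does not cover the Day 214-234 draw window, and vaccines or steroids taken after about Day 84 may go unrecorded before the Day 224 immune samples

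*Protocol*

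**What the plan says.** **Washout.** Protocol Section 5.2, criterion 10 (repeated in SAP Section 4), asks for "no planned immunizations between Day 0-84 or Day 210-224 due to the washout period prior to immunology blood draws". The stated purpose is to protect the immunology samples.

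**Visit window.** The late draw belongs to "7.9 Day 224 (± 10) Evaluations", so it may be taken on Days 214 to 234. Appendix 1 gives the same window.

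**Medication collection.** Section 6.5 opens with an undated statement that vaccines, among other treatments, will be documented. It then limits concomitant medications to those taken from 30 days before enrollment "through 28 days after the last study injection (approximately Day 84) or early termination, whichever occurs first". Section 8.1 says "through 28 days after the last study injection, unless if used for treatment of an SAE or PIMMC". The Day 224 procedures in Section 7.9 read "Record concomitant medications used for treatment of SAEs or PIMMCs, if any", and Appendix 1, footnote 6, reads "Concomitant meds to be collected only if used for treatment of an SAE or PIMMC".

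**Use of Day 224.** Section 3.2.2 lists Day 224 for every secondary immune outcome, for example "Mean fold change from baseline (Day 0) in IgG antibody responses to ID93 on Days 14, 56, 70, 84, and 224". It is the only secondary time point after Day 84, because Day 421 is a telephone contact (Section 7.10).

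**Analysis set.** SAP Section 7.2.1 analyses immune response in the per-protocol population. SAP Section 5 defines this by eligibility and receipt of both injections.

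**The concern.** The sponsor judged that a recent vaccine could disturb these assays and wrote a rule to prevent it. The rule is fixed to study days, while the draw it protects can move by 10 days either way. For most permitted visit days the rule therefore does not give the separation it implies at the nominal visit. It also speaks only of planned immunizations.

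The second half is detection. Before enrolment the protocol excludes recent tuberculin skin tests, immunosuppressive medication and vaccines (criteria 5, 7 and 10). Between about Day 84 and Day 224 no scheduled procedure asks about any of them unless the drug treats an SAE or PIMMC. Non-serious adverse events also stop being collected at Day 84 (Section 4), so an ordinary illness treated with a steroid course would leave no routine trace. If an exposure is not recorded, the affected sample cannot be found at analysis. The durability reading at Day 224 then carries an unknown contribution from events unrelated to the study vaccine.

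**Working it through.** **Inputs.** Vaccine-free interval Days 210-224 (Section 5.2). Day 224 visit window ±10 days (Section 7.9). Day 84 visit window ±5 days (Section 7.8). Arm sizes 25 and 23 (SAP Table 1).

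**The plan's own interval.** 224 − 210 = 14 days before the nominal visit.

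**Permitted visit days.** 224 − 10 = 214 and 224 + 10 = 234, which is 234 − 214 + 1 = 21 days.

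**Shortest gap that the rule allows.** For a draw on day *v*, take the latest earlier day, after Day 84, that lies outside Days 210-224. Up to *v* = 225 that is Day 209, so the gap is *v* − 209. From *v* = 226 it is Day *v* − 1, so the gap is 1.

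| Day of draw | Number of days | Latest permitted vaccination before it | Gap |
|---|---|---|---|
| 214 to 222 | 9 | Day 209 | 5 to 13 days |
| 223, 224, 225 | 3 | Day 209 | 14, 15, 16 days |
| 226 to 234 | 9 | the day before the draw | 1 day |

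A gap of at least 14 days is guaranteed on 3 of 21 visit days (14%). The other 9 + 9 = 18 days (86%) allow a shorter one.

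**Sensitivity to the counting rule.** The table leaves out vaccination on the day of the draw. If that is counted, Day 225 also fails and 2 of 21 days remain (223 and 224). If the gap must exceed 14 days, Day 223 fails, leaving Days 224 and 225, or Day 224 alone when same-day vaccination is counted as well. Under any of these conventions at least 18 of 21 days fail.

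**Day 84.** The first restriction ends at Day 84 but the draw may be as late as 84 + 5 = Day 89, so draws on Days 86-89 allow a vaccine the day before. Section 7.8 reviews concomitant medications at that same visit, so such a vaccine has a route into the record.

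**Would the analysis remove an affected Day 224 sample?** A vaccine on Day 209 or Day 233 does not breach criterion 10, so it need not be a protocol deviation. The per-protocol definition does not mention such exposures, and the SAP plans no sensitivity analysis for them.

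**Weight of one subject.** 1/25 = 4.0% and 1/23 = 4.3% of an arm's Day 224 response rate.

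**Room to move a draw.** A draw at least 14 days after a vaccine on day *d* fits the window only if *d* + 14 ≤ 234, that is *d* ≤ 220. For Day 221, 221 + 14 = 235, which is outside it.

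**The case against.** The strongest opposing case is that this is a phase 1 trial with no formal hypothesis (Section 11.3), that one late secondary time point is affected, and that neither the frequency nor the effect of these exposures is known. The assay readouts are also specific to ID93, and the cellular ones are background-subtracted. That limits how much weight the point can bear, but it does not make the washout match the window.

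Four stronger readings are tempting and are not supported:

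- *The comparison of presentations is confounded.* Assignment is randomized and double-blind, so intercurrent exposure should fall evenly on average. What remains is noise and chance imbalance.
- *Nothing is asked after Day 84.* Treatments for an SAE or PIMMC are recorded at Days 224 and 421, and unscheduled visits review medications (Section 7.12). Section 6.5 discourages glucocorticoids and immunosuppressive drugs without an end date, and its opening sentence names vaccines. That sentence conflicts with the Day 84 limit in the same section, and no Day 224 procedure carries it out.
- *The rule is checked only at enrolment.* Section 5.3 requires the eligibility criteria, apart from safety laboratory values, to be met again before the second injection, and Section 7.5 schedules that review. It falls at Day 56, well before the late draw.
- *The Day 84 draw is equally exposed.* The medication review at that visit largely answers this.

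The SAP also defines an Immunogenicity Population free of major protocol deviations. SAP Section 7.2.1 names the per-protocol set instead, and in any case a permitted or unrecorded exposure would not count as a deviation.

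**Conclusion.** The mismatch is real and follows from the protocol's own dates. The gap between a permitted vaccine and the Day 224 draw can be as short as 5 days for an early visit and 1 day for a late one, and 14 days is guaranteed on 3 of 21 visit days. The recording gap is also real, in the limited sense that exposures other than SAE or PIMMC treatment are not routinely collected at scheduled visits after about Day 84 and so may be missed.

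The main consequence is for the within-arm Day 224 change from Day 0. For the comparison between arms it is mostly extra variability, with one subject worth about 4% of an arm.

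The conclusion assumes that the 14 days implied at the nominal visit is the separation intended; the protocol gives no reason for that length, so it cannot be checked. The actual distribution of visit days, the rate of exposure and its effect on ID93 responses are not given, so no bias can be computed. This is a modest inconsistency that is cheap to repair, and it does not invalidate the Day 224 results.

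**What to change.** 1. **Reconcile the passages.** Bring the washout interval (Protocol Section 5.2, SAP Section 4), the visit window (Section 7.9, Appendix 1) and the collection rules (Sections 6.5, 7.9, 8.1 and Appendix 1, footnote 6) into agreement. Define the on-study washout relative to the actual Day 224 draw date. Keep criterion 10 as a check of plans, since the draw date is unknown at entry.
2. **Ask once.** At the existing Day 224 visit, add one question on vaccines, tuberculin skin tests and systemic steroid or immunosuppressant use since Day 84, with dates.
3. **Analyse.** In SAP Section 7.2.3, repeat the Day 224 comparison without samples drawn inside the washout or under immunosuppression.
4. **Flag where a draw cannot move.** If the draw cannot be moved within the existing window, flag the sample rather than reschedule it.

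SAP Section 1 says that the safety analysis is done and that the amendment concerns immunology only, so the Day 224 visits may already be complete. In that case the SAP can still compare actual collection dates with any exposures found in source documents, and the report should state the limitation.

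The cost is one question, one sensitivity analysis, and a few visits moved or samples flagged.
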